- v* Investigator will examine each participant's joints per the Haemophilia Joint Health Score (HJHS). At baseline, the Investigator will assess the presence of any target joints according to the International Society on Thrombosis and Haemostasis (ISTH) criteria.
- w* For bleeding episodes initially treated at the study sites, the Investigator will contact the caregiver approximately 72 hours from the time the BIVV001 injection was administered to treat the bleeding episode at the study site and record the caregiver's assessment of response to BIVV001 treatment on the eCRF using a 4-point bleeding response scale. For bleeding episodes that are treated at home, caregivers will record response to bleeding episodes in the ePD.
- x* Samples will be collected prior to any BIVV001 dosing and will be archived by the central laboratory (if required) for future research, eg, immunology assays, further coagulation assays, or clarification of any clinical or laboratory AE, etc. This is optional and participants/caregivers will sign an additional consent for this research.
- y* At the screening visit, caregivers will be shown and trained on the ePD device to ensure understanding of obligation to enter data during the trial. Devices will be given to caregivers at the baseline visit.
- z* Caregivers will record all bleeding episodes in the ePD beginning at Baseline. Assessment of response to bleeding episodes will be performed using a 4-point bleeding response scale. The caregiver should record response approximately 72 hours from the time the first BIVV001 injection was administered to treat the bleeding episode, unless treatment of the bleed was administered in the clinic. In that case, the investigator will report the caregiver's response to treatment via the eCRF.
- aa* The first 12 participants in each age cohort will undergo PK sampling after the first dose of BIVV001 (Baseline). Thereafter, PK sampling at Baseline will be optional. See PK sampling details in [Table 2](#).
- bb* Trough and peak samples are collected within 30 minutes prior to rFVIIIFc-VWF-XTEN dosing and 15 (\pm 3) minutes post-injection, respectively. This trough sample should be collected at the same time point as the trough inhibitor and ADA samples taken predose.

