
 To evaluate the efficacy of BIVV001 as a prophylaxis treatment To evaluate the efficacy of BIVV001 in the treatment of bleeding episodes To evaluate BIVV001 consumption for prevention and treatment of bleeding episodes To evaluate the effect of BIVV001 prophylaxis on joint health outcomes To evaluate the effect of BIVV001 prophylaxis on Quality of Life (QoL) outcomes To evaluate the efficacy of BIVV001 for perioperative management 	
 Annualized bleeding rate (ABR) (for treated, for untreated, for all bleeding episodes) and by type and location Percentage of participants who maintain FVIII activity levels over 1%, 3%, 5%, 10%, 15%, and 20% at Day 7 Number of injections and dose of BIVV001 to treat a bleeding episode Percentage of bleeding episodes treated with a single injection of BIVV001 Assessment of response to BIVV001 treatment of individual bleeding episodes based on the International Society on Thrombosis and Haemostasis (ISTH) 4-point response scale Physician's global assessment (PGA) of participant's response to BIVV001 treatment based on a 4-point response scale Total annualized BIVV001 consumption per participant Annualized joint bleeding rate (AJBR) Target joint resolution at Week 52, based on ISTH criteria Change from Baseline to Week 52 in total score and domain scores (eg, swelling and strength) assessed by the Hemophilia Joint Health Score (HJHS) Changes in Haemophilia Quality of Life Questionnaire for Children (Haemo-QoL) total score and physical health domain score from baseline to Week 52 (≥4 years old) and via parent proxy version (≥4 years old) Investigators' or Surgeons' assessment of participant's hemostatic response to BIVV001 treatment on the ISTH 4-point response for surgical procedures scale Number of injections and dose to maintain hemostasis during perioperative period for major surgery Total BIVV001 consumption during perioperative period for major surgery Number and type of blood component transfusions used during perioperative period for major surgery Estimated blood loss during perioperative period for major surgery

Objectives	Endpoints

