The first 12 participants in each age cohort (<6 years of age to 12 years and 6 to <12 years of age) will undergo PK sampling after the first dose of BIVV001 (Baseline) (see [Table 2](#) for details). After full enrollment of the PK subgroup, optional participation in the PK subgroup is offered. All other participants will have trough and peak samples only (collected within 30 minutes prior to BIVV001 dosing and 15 (\pm 3) minutes post injection).

Participants who undergo major surgery during the study will be included in the surgery subgroup.

Study clinic visits

All enrolled participants will come in to scheduled visits at the following time points: Baseline (Day 1), Week 4, Week 13, Week 26, Week 39, and Week 52. Details of each visit are provided in [Table 1](#).

For all participants each scheduled study visit subsequent to BIVV001 Day 1 is to be arranged 7 days (\pm 1 day) after the preceding prophylaxis dose. The participant should withhold the weekly prophylaxis dose on the day of the study visit, so that it can be administered at the study visit.

The first 12 participants in each age cohort (<6 years of age to 12 years and 6 to <12 years of age) will undergo PK sampling after the first dose of BIVV001 (Baseline), including samples at Day 1, Day 2, Day 4 and Day 8 (Table 2). All other participants will have trough and peak sample only (collected within 30 minutes prior to BIVV001 dosing and 15 (\pm 3) minutes post-injection at each visit where a BIV001 injection is scheduled.

Participants will undergo efficacy and safety assessments throughout their participation in the study. Safety assessments will include testing for inhibitor development to FVIII. A Follow-up Safety Visit or Telephone Call will occur 2 to 3 weeks after the last dose of BIVV001, unless the participant enrolls in the open-label extension study. Participants will complete their End of Study (EOS) Visit 52 (\pm 7) days post-Baseline, or earlier if EOS has been declared.

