6.1.2 Study treatment schedule and administration

Instructions for the preparation and administration of BIVV001 are provided in the Pharmacy Manual and the Information for Patients.

The prophylactic treatment regimen is QW (every 7 days) dosing with 50 IU/kg BIVV001. This dose was determined based on population PK model and appropriate simulations to understand steady state kinetics of BIVV001. The aim of the 50 IU/kg QW treatment regimen is to provide sustained FVIII activity levels in the normal to mild hemophilic range and to decrease treatment burden with QW dosing.

The dosing interval in the younger age cohort (<6 years) may be reduced by 1 or 2 days if clinically warranted at the discretion of the investigator and only after consultation with the study medical monitor. For participants who have their BIVV001 dosing interval reduced, the washout period prior to inhibitor tests must be adjusted accordingly.

BIVV001 will be delivered via a slow push IV injection at a rate of administration listed in [Table 6](#) and determined by the participant's comfort level. BIVV001 formulation contains sucrose and the injection durations listed in [Table 6](#) are consistent with recommendations on infusion rates. Overall, the recommended maximum total injection time should be ≤ 15 minutes for all doses.

Table 6 - BIVV001 weight-based vial and injection rate recommendations

Participant weight	Minimum injection duration per vial	Maximum total injection time
10-<20 kg	6 minutes per vial	15 min
20-<30 kg	3 minutes per vial	15 min
≥ 30 kg	2 minutes per vial	15 min

Any missed of BIVV001 doses should be taken as soon as possible or according to the instructions of the Investigator, taking into account that 2 consecutive prophylactic doses of 50 IU/kg should be separated by a period of at least 72 hours.

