Embolic and thrombotic events are defined as arterial or venous thrombosis, confirmed by imaging.

Coronary artery thrombosis/occlusion must be confirmed by coronary angiography to be included as part of medical adjudication.

Thrombosis involving the cerebral vasculature must be confirmed by imaging such as magnetic resonance imaging venogram, computed tomography venogram, magnetic resonance angiography, or computed tomography angiography to be included as part of medical adjudication.

An indwelling central venous access device is a well-established risk factor for thrombosis (47) and thrombotic events associated with such devices will not be included as part of medical adjudication. Occlusion or malfunction of a central venous access device also will not be included as part of medical adjudication.

Infusion thrombophlebitis is a recognized complication of peripheral vein infusion (48) and will not be included as part of medical adjudication.

Pharmacokinetics

Any participant with adequate BIVV001 PK data will be included in the PK Analysis Set. A noncompartmental analysis will be performed for each participant's BIVV001 baseline PK profile. At least 24 participants will be enrolled in the PK group. Instructions for wash-out and PK sampling are provided in Appendix 7, [Section 10.7.4](#).

Pharmacokinetic parameters of BIVV001 activity including but not limited to C_{max} , CL, CL_{ss} , V_{ss} , AUC, DNAUC, MRT, IR, C_{trough} and time above 1% FVIII activity measured by aPTT clotting assay and chromogenic assay will be determined for BIVV001. Pharmacokinetic parameters will be summarized for each age cohort for BIVV001 with geometric means and their corresponding 95% CIs.

Other Secondary endpoints

All other secondary endpoints will be summarized descriptively.

The number and percentage of participants achieving trough FVIII activity levels above 1%, 3%, 5%, 10%, 15%, and 20% will be summarized. In these summaries, FVIII activity level will be based on the average trough samples (ie, nominal 168 hour time point) from each scheduled visit (Week 4, Week 13, Week 26, Week 39, Week 52) using the one-stage aPTT assay and chromogenic assay. Participants with trough samples that are outside 168 ± 5 hours from the previous dose will be excluded from this analysis.

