4.4.4 Percentage of participants who maintain FVIII activity levels

The number and percentage of participants achieving steady-state trough FVIII activity levels above 1%, 3%, 5%, 10%, 15%, and 20% will be summarized by age cohort and overall. In these summaries, FVIII activity level will be based on the average trough samples (ie, nominal 168-hour time point) from each scheduled visit (Week 4, Week 13, Week 26, Week 39, Week 52) using the aPTT-based one-stage assay and chromogenic assay. Participants with trough samples that are outside 168 +/-5 hours from the previous dose will be excluded from this analysis.

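### The 168 ± 5 h rule excludes participants rather than samples, so children under 6 with a shortened dosing interval may drop out of the Day-7 FVIII endpoint even when they have valid earlier troughs

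*Protocol*

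**What the plan says.** On the interval, Protocol 6.1.2 states: "The dosing interval in the younger age cohort (<6 years) may be reduced by 1 or 2 days if clinically warranted". This is at the investigator's discretion after consulting the medical monitor. The section then adds: "For participants who have their BIVV001 dosing interval reduced, the washout period prior to inhibitor tests must be adjusted accordingly".

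On the sample, Table 1 footnote bb (Protocol 1.3) places the trough just before dosing and says: "This trough sample should be collected at the same time point as the trough inhibitor and ADA samples taken predose".

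On the endpoint, Protocol Section 3 lists: "Percentage of participants who maintain FVIII activity levels over 1%, 3%, 5%, 10%, 15%, and 20% at Day 7". The SAP's objectives table omits the Day 7 wording, but SAP 4.4.4 keeps the time point: "FVIII activity level will be based on the average trough samples (ie, nominal 168-hour time point) from each scheduled visit", the visits being Weeks 4, 13, 26, 39 and 52.

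On exclusion, SAP 4.4.4 says: "Participants with trough samples that are outside 168 +/-5 hours from the previous dose will be excluded from this analysis". Protocol 9.4.3 has the same rule: "Participants with trough samples that are outside 168 ± 5 hours from the previous dose will be excluded from this analysis". Neither document makes an exception for a shortened interval.

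On visit timing, Protocol 4.1 says: "For all participants each scheduled study visit subsequent to BIVV001 Day 1 is to be arranged 7 days" after the preceding dose, give or take one day. Table 1 footnotes c and j and Protocol 10.7.4 also use 7 ± 1 days. None of these mentions shortened intervals.

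**The concern.** The endpoint asks how many children hold FVIII above each of six thresholds a week after a dose. A child whose interval was shortened has left weekly dosing, and a predose sample at the new interval can no longer be a 168 h sample. The written rule then drops the child, not just the sample, and any valid troughs from before the change go too.

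The change is made on clinical grounds. If those grounds are linked to low FVIII or to bleeding, the children who remain are a favourable selection. The youngest cohort's percentage, and through it the overall figure, would then look better than weekly dosing achieved.

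**Working it through.** The plan states no figure for this point, and its sample size is not statistical, so there is nothing to reproduce. The check compares times and then bounds the effect.

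**1. Sampling times.** The accepted window is 168 − 5 = 163 h to 168 + 5 = 173 h. The visit rule of 7 ± 1 days is 144 to 192 h.

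| Interval | Predose sample | Within 163–173 h? | Within 144–192 h? |
|---|---|---|---|
| 7 days | 168 h | yes | yes |
| 6 days | 144 h | no, 163 − 144 = 19 h early | yes, at the edge |
| 5 days | 120 h | no, 163 − 120 = 43 h early | no |

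Sampling at the new interval follows from reading 6.1.2 together with footnote bb. No passage says it outright.

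**2. What the unit of exclusion does.** Take a child shortened after a valid Week 4 trough. Under the literal wording the child is removed. With the window applied per sample, the child stays in on the Week 4 value and only later samples drop out. A child shortened before Week 4 has no valid scheduled trough on either reading. If in the PK subgroup, that child would normally still have a 168 ± 5 h sample on Day 8 after the first dose (Protocol Table 2).

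**3. Can an early sample stand in for Day 7?** No. Protocol 2.2.3.2 gives adult steady-state means on 50 IU/kg weekly of 22% on day 5 and 9% on day 7, a ratio of 22/9 = 2.4. Log-linear interpolation puts day 6 at √(22 × 9) ≈ 14%.

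**4. Direction and size.** Let p be the true share above a threshold, f the share of children excluded for a shortened interval, and q the share of those excluded who are above it. Then

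reported share = (p − f·q) / (1 − f).

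The documents give none of p, f or q. The values below are assumptions, using the target of 25 children under 6.

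- q = 0, p = 80% (20 of 25): one excluded, 20/24 = 83.3%; three, 20/22 = 90.9%; five, 20/20 = 100%.
- q = 0, p = 10%, three excluded (f = 3/25 = 12%): 0.10/0.88 = 11.4%, a shift of 1.4 points.
- q = p = 80%, five excluded, four of them above: 16/20 = 80%, no shift.

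The percentage is overstated only if q is below p, and the amount depends on the threshold.

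**5. Worst-case bound.** Suppose k of 25 have no usable value and all others are above the threshold.

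| k | Excluded | Counted as not maintaining (Clopper-Pearson 95% CI) |
|---|---|---|
| 1 | 24/24 = 100% | 24/25 = 96% (79.6–99.9) |
| 3 | 22/22 = 100% | 22/25 = 88% (68.8–97.5) |
| 5 | 20/20 = 100% | 20/25 = 80% (59.3–93.2) |

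**6. The rule reaches further.** The accepted window is 10 h wide inside a permitted visit window of 48 h, or 10/48 = 21% of it. A weekly-dosed child in either cohort who attends on an allowed day can also be off-window, and the participant-level wording can remove that child too.

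**The case against.** The case for leaving the rule alone has four parts.

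- **The target is a 168 h trough.** Limiting the analysis to valid 168 h samples is a sound choice. This stands, but it justifies dropping samples, not a child's earlier valid ones.
- **The visits are set at 7 ± 1 days for everyone.** On that view the early samples might not arise. This stands in part: the timing is an inference. A 6-day interval meets the visit rule at 144 h and still misses the analysis window. Only the 5-day interval breaks the visit rule, and keeping such a child to 7 days would sit badly with the adjusted washout in 6.1.2.
- **The information appears elsewhere.** SAP 4.8.1 summarises troughs by visit for the full analysis set with no time window stated, and SAP 4.7.1.2 tabulates interval compliance. The first mixes 120, 144 and 168 h samples. The second allows 36 h either side of 7 days, so a 6-day interval (24 h off) counts as compliant and only a 5-day one (48 h off) shows. Neither is linked to this endpoint.
- **The endpoint is secondary and descriptive, with no test.** This stands and limits the consequence.

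A reader might go further and infer that the excluded children are those in whom weekly dosing failed. The documents do not say so: the trigger is undefined and is not tied to an FVIII level. A child shortened because of bleeding could still be above 1% or 3% at Day 7.

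**Conclusion.** The point holds in a limited form. As written, the rule can remove children under 6 from the Day-7 endpoint because their interval was shortened, including children with valid earlier troughs. This rests on two things: the literal participant-level wording, and predose sampling at the new interval. The exclusion may be informative. Overstatement of the under-6 and overall percentages is the plausible direction, but its size cannot be stated, because neither document gives the number of interval changes.

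Three stronger conclusions are tempting and not supported:

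- **That the reported figure would rise from 80% to between 83% and 100%.** This needs every shortened child to be below the threshold. Other equally allowable assumptions give a shift of 1.4 points or none.
- **That applying the window per sample would not help.** It keeps every child who has a valid trough from before the change, and leaves only those without one.
- **That failure is the only value that can be assigned to a child with no valid scheduled trough.** PK-subgroup children normally have a measured 168 h value on Day 8. Counting a child as failing at all six thresholds is a bound, not an estimate.

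**What to change.** In SAP 4.4.4, and in Protocol 9.4.3 if it is amended:

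1. Apply the 168 ± 5 h window to samples. Average each participant's valid troughs, keeping those from before any interval change. This also helps weekly-dosed children who have a single off-window sample.
2. Do not use 120 or 144 h samples as Day-7 values.
3. Report by cohort how many participants have no valid trough, and how many of these had a shortened interval.
4. Add a sensitivity line, labelled a worst-case bound, in which shortened-interval children with no valid scheduled trough stay in the denominator as not maintaining. Where a Day 8 168 h value exists, show it beside this line as supporting data. It follows a first dose, whereas SAP 4.4.4 is about steady state.
5. Reconcile the 7 ± 1 day visit and washout rules (Protocol 4.1, Table 1 footnotes c and j, 10.7.4) with the adjusted washout in 6.1.2, so that the sampling time for a shortened interval is unambiguous. Which rule should govern is for the sponsor to settle.

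Items 1 to 4 cost SAP wording, the counts and one extra table line, with no new data. The downside is that the under-6 percentages may come out lower.

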6.1.3 Treatment of bleeding episodes during prophylactic treatment regimen

The participant's caregiver will be instructed by the clinic on how to treat a bleeding episode at home and record this in the ePD (for a definition of bleeding episode refer to [Section 8.1.2](#)). Bleeding episodes requiring treatment will be treated with a single dose of 50 IU/kg, as described in [Table 7](#).

Major bleeding episodes will be treated in the hospital/clinic or at home, as applicable. The participant's caregivers will be instructed to consult the investigational site prior to dosing any follow-up injection. Administration of a second dose of BIVV001 as follow-up treatment will be determined by the Investigator and participant's caregivers based on the participant's clinical condition. If a bleed does not improve, additional doses of 30 or 50 IU/kg every 2 to 3 days may

be considered. For mild/moderate bleeds within 2-3 days of a recent prophylactic dose, a 30 IU/kg dose may also be used. Treatment of any bleeding reported within 72 hours of a previous episode at the same location should be considered a follow-up injection and the event should not be recorded as a new bleeding episode. If a bleeding episode occurs at the time when a regular prophylaxis dose of BIVV001 is due, the participant will inject with a dose of 50 IU/kg.

Resumption of prophylaxis dosing following treatment for bleeding episodes is outlined below:

If the bleeding episode is stopped with a single dose of 50 IU/kg BIVV001, the participant will continue with the schedule of weekly prophylaxis dosing he was on prior to the bleeding episode, unless the next scheduled prophylaxis dose is within 72 hours of the treatment of the bleeding episode. In this case, the prophylaxis dose should be delayed until 72 hours after last 50 IU/kg dose for treatment of the bleeding episode. Thereafter, the participant should return to the schedule of weekly prophylaxis dosing that he/she was on prior to the bleeding episode. If the participant needs additional doses of 30 IU/kg after the first 50 IU/kg dose to treat a bleeding episode, these additional doses will not require any further delay of the next prophylaxis dose.

6.1.4 Surgical dosing

Minor surgeries can be performed while participating in this trial by administering a dose of 50 IU/kg BIVV001 ([Table 7](#)).

Participants who undergo major surgery during the study will be included in the surgery subset. Definitions for major and minor surgery are listed in Appendix 7, [Section 10.7.1](#).

Prior to surgery, the Investigator will plan the perioperative treatment regimen of FVIII replacement therapy generally required for the type of planned surgery in accordance with the dosing guidance in [Table 7](#). Recommendation for the appropriate dosing of BIVV001 in the surgical treatment period, including any rehabilitation time, will be discussed among the Investigator, Surgeon, and Sanofi BIVV001 Medical Monitor. No continuous infusion of BIVV001 will be allowed for this study.

For all participants in the surgery subgroup, the surgical period will begin with their first dose of BIVV001 given for the surgery (ie, the pre-operative loading dose) of 50 IU/kg IV. If needed, the dose level of BIVV001 should be adjusted to aim for a FVIII activity level of at least 100% and maintained during the surgery according to the WFH Guidelines.

Post-operatively, FVIII activity levels should be monitored by daily measurements of FVIII activity locally as long as the patient is hospitalized. FVIII levels should be maintained at recommended levels and duration according to WFH Guidelines. Depending on the targeted FVIII activity level this likely means a need to administer a second dose approximately 48-72 hours after the pre-operative loading dose. Additional doses of 30 or 50 IU/kg every 2 to 3 days may be administered depending on the desired FVIII activity levels and the severity of the procedure. Due to the long $t_{1/2}$ of BIVV001, the frequency of dosing in the post-surgical period may be extended after the first week post-surgery.

Table 7 - Intravenous BIVV001 treatment

Indication	Dosage	Frequency
Prophylaxis	50 IU/kg	Once weekly
Bleeding episode ^a	50 IU/kg	Single dose for all bleeding episodes. Additional and adjusted doses only after consultation with the Investigator: If a bleeding episode does not improve, additional doses of 30 or 50 IU/kg every 2 to 3 days may be considered. For minor/moderate bleeding episodes within 2 to 3 days of a recent prophylactic dose, a 30 IU/kg dose may also be used.
Minor surgery	50 IU/kg	Single dose prior to surgery
Major surgery, only allowed after 6 EDs	50 IU/kg	Additional doses of 30 or 50 IU/kg every 2 to 3 days may be administered.

^a Refer to Appendix 7 (Section 10.7.2) for definitions of minor, moderate, and major bleeding episodes.

6.1.5 Bleeding episodes that occur prior to the baseline and during PK sampling period

If a participant experiences a bleeding episode during the washout period before PK sampling in conjunction with their first dose of BIVV001, the participant should treat the bleeding episode with their pre-study FVIII product. A participant who experiences a bleeding episode in the dosing interval prior to a scheduled visit to monitor trough PK levels should be treated with BIVV001 using the treatment guidelines described in [Table 7](#).

Detailed guidelines for washout and sampling details are provided in Appendix 7, [Section 10.7.4](#).

